## LIST OF ABBREVIATIONS

COI	Conflict of Interest
DHHS	Department of Health and Human Services
DMC	Data Monitoring Committee
DSMB	Data and Safety Monitoring Board
DSMP	Data and Safety Monitoring Plan
FERPA	Family Educational Rights and Privacy Act
FDA	Food and Drug Administration
GCP	Good Clinical Practice
HIPAA	Health Insurance Portability and Accountability Act
IBC	Institutional Biosafety Committee
ICD	Informed Consent Document
ICH	International Conference of Harmonization
IDE	Investigational Device Exemption
IDS	Investigational Drug Service
IND	Investigational New Drug
IRB	Institutional Review Board
LAR	Legally Authorized Representative
OHRP	Office of Human Research Protections
OPRS	Office for the Protection of Research Subjects
PHI	Protected Health Information
PI	Principal Investigator
PPRA	Protection of Pupil Rights Amendment
QA/QI	Quality Assurance/Quality Improvement
SAE	Serious Adverse Event
SOP	Standard Operating Procedure

## 1.0 Project Summary/Abstract

This study has been revised to allow for maximal social distancing in order to expedite the study time line, minimize risk of COVID19 exposure, and ensure participant safety.

The Latino population over age 65 will reach 18% of the total U.S. population by 2050. Currently, over 12% of older adult Latinos have been diagnosed with Alzheimer's disease and related dementias (ADRD). Even more striking, the number of Latinos with ADRD is expected to increase 9-fold over the next 3 decades, representing an epidemic increase of ADRD. The high incidence of ADRD in conjunction with physical function limitations place older Latinos at a high risk for loss of independence and significant caregiver burden. Sedentary time (defined as sitting) has been shown to be associated with reduced cognitive function in healthy older Latinos. Studies are clearly needed to investigate the benefits on cognition and brain connectivity of breaking up and replacing sedentary time with physical activity (PA) in older Latinos. However, in order to develop and deliver a successful intervention we need to understand how to best conduct a lifestyle intervention in the Latino community. Our current understanding is rooted in a Eurocentric view that assumes that interventions that work in one community will work the same way in a different community. This assumption is likely incorrect and represents a significant gap in our ability to develop a successful intervention at the multiple levels that are required across the socio-ecological model (SEM) to be successful. We propose to investigate the interactive effects of behavior determination to increase PA levels in older Latinos. This study will examine factors that facilitate initiation of and adherence to behavioral change at the individual level using the social cognitive theory, and ecological momentary assessment in an inner-city Chicago Latino Senior community. Our objectives are: 1) to discern the individual characteristics and the social networks within the community that influence behavior change to increase PA levels in the Latino community. 2) To assess the feasibility and acceptability of our PA measures. 3) To test the feasibility and initial impact of an intervention program designed to replace sedentary time with PA that has been designed specifically for older Latinos and delivered at home, to improve cognitive function and brain connectivity. We will achieve these objectives by using phone interviews, ecological momentary assessment, and an ecological momentary intervention within an inner city Chicago Latino senior community. Findings will directly facilitate the development and progression of culturally appropriate intervention(s) that will lead to rapidly translatable programs for older adults at risk for cognitive and physical decline. **This proposal is very relevant to ADRD and aging research** and addresses several areas of focus. 1). Physical Activity promotion, creation, modification and pilot testing of a principle-based intervention to reduce sedentary behavior and increase physical activity. 2). Pilot testing an intervention to enhance mobility in older adults to improve cognitive and physical functioning to prevent or forestall loss of independence. 3). We are harnessing technology to *promote and sustain* a behavioral intervention to achieve healthy aging in older adults.

## 2.0 Background/Scientific Rationale

The Latino population over age 65 will comprise 18% of the total U.S. population by 2050. Currently, over 12% of older adult Latinos have been diagnosed with Alzheimer's disease and related dementias (ADRD). Even more striking, the number of Latinos with ADRD is expected to increase 9-fold over the next 3 decades, representing an epidemic rate of increase. The high incidence of ADRD in conjunction with physical function limitations place older Latinos at a high risk for loss of independence and significant caregiver burden. Sedentary time (defined as sitting) is a known risk factor for reduced cognitive function in healthy older Latinos. Studies are clearly needed to investigate the benefits on cognition and brain connectivity of breaking up and replacing sedentary time with physical activity (PA) in this population. However, in order to develop and deliver a successful intervention we need to understand how to best conduct a lifestyle intervention in the Latino community. We propose to investigate the interactive effects of behavior determination to increase PA levels in this population. This study will examine factors that facilitate initiation of and adherence to behavioral change at the individual level using social cognitive theory, and ecological momentary assessment in an inner-city Chicago Latino Senior community.

## 3.0 Objectives/Aims

Successful lifestyle interventions must act on multiple levels across the SEM in order to in order to increase daily physical activity. The SEM underscores the importance of understanding how the individual and the individual's interpersonal community affect behavior change. Our long-term goal is to develop an intervention that is specifically tailored to older Latinos to *prevent or forestall cognitive and physical function decline*. Specifically, we propose to investigate the interactive effects of behavior determination to increase physical activity (PA) levels in older Latinos. Our objectives are

- 1) to discern the individual characteristics and the social network within the community that influence behavior change to increase PA levels in an inner city Chicago Latino community.
  - 2) To assess the feasibility and acceptability of our PA measures.
  - 3) To test the feasibility of an intervention designed to replace sedentary time with PA that has been designed specifically for older Latinos and delivered in their homes to improve cognitive function.
- **Aim 1 (stage 1A):** Conduct individual phone interviews to determine the individual characteristics and the social networks that influence behavior change to reduce and replace sedentary time with PA within an older adult Chicago Latino community. The focus groups will be 50% male and 50% female to enable comparisons of possible gender-differences.
- **Aim 2 (stage 1A):** Assess the feasibility and acceptability of our PA measures and ecological momentary assessment (EMA) in this community.

- **Aim 3 (stage 1B):** Determine the feasibility and acceptability of an ecological momentary intervention (EMI) program designed to reduce and replace sedentary time with PA in older Latinos, delivered in the home-setting over 6 weeks, compared to participants randomized to receive physical activity guidelines in Spanish.
- **Exploratory aims (stage 1B):** To explore the feasibility and preliminary effect of the EMI intervention on cognitive function in older Latinos, compared to participants randomized to guidelines.

**Study Duration:** This is a feasibility pilot randomized, controlled trial of a 6-week intervention. Outcome measures will be obtained at baseline and at 6-weeks. Behavior choices and preference data will be continuously captured during the intervention.

#### **4.0 Eligibility**

We will randomize 80 older Latinos from a Chicago Latino community center to either the EMI intervention (n=40) or to physical activity guidelines (n=40).

[name] or study designee will assess and determine the subject eligibility. An eligibility checklist will be completed prior to any study participant randomization. Eligibility criteria will be continuously monitored by the PI/RA and document via an eligibility checklist at the baseline and follow-up.

##### **4.1 Inclusion Criteria**

- Men and women >55-89 years of age, no history of major head trauma, ownership of a working smartphone, and ability to use video calls.

##### **4.2 Exclusion Criteria**

- No ability to use video technology
- Wheelchair dependent
- Diagnosed dementia,
- Participating in a supervised exercise program with intent to increase fitness levels 3 days/week,
- Contraindications to PA per ACSM
  - Requires assistive ambulation;
  - Unstable angina,
  - Claudication
  - severe arthritis,
  - extreme dyspnea on exertion,
  - Class III-IV heart failure;
  - Current uncontrolled sustained arrhythmias,
  - severe/symptomatic aortic or mitral stenosis,
  - hypertrophic obstructive cardiomyopathy,
  - severe pulmonary hypertension,
  - active myocarditis/pericarditis,
  - thrombophlebitis,
  - recent systemic/pulmonary embolus (within 3 months);
  - Revascularization procedures within the previous 6 months;

- Pregnancy

#### **4.3 Excluded or Vulnerable Populations**

Vulnerable populations are not included in this study.

The following populations are excluded from this study: 1. Pregnant women: Pregnant women are excluded to limit any potential influence on measures.

Non-English speaking population: Non-English speaking population other than Spanish will be excluded from the study.

Spanish speaking population will be included once IRB approval has been obtained for the Spanish translated versions of the consent, phone app, and study documents.

### **5.0 Subject Enrollment**

Participants are community dwelling adults without dementia. We have established strong relationship with this organization and key stakeholders. Participants will be recruited through a flyer with information about the study posted on organization's website and by word of mouth. We have developed a media recruitment script that will be used as the script for a video presentation that will be posted on a website, TV add, Facebook, and read as a radio add. We will send a notice via the CCTS research match and the TNN Match service using the form titled "research match".

- Participants that contact the study team will be sent the consent form and given as much time as they feel necessary to decide if they would like to participate. Participants will be encouraged to ask any questions at any time throughout the course of the study. Research personnel will be available to answer these questions. Subjects will be informed that participating in this research is voluntary. Subjects will be informed that they may withdraw from the research at any time without penalty. Patient providers are not part of the study team.

### **6.0 Study Design and Procedures**

This research will be performed via telephone/video conference to maximize social distancing and participant safety. The intervention will be performed by the participants at home.

This is a pilot randomized, controlled trial of a 6-week intervention for feasibility. Outcome measures will be obtained at baseline and at 6-weeks. Behavior choices and preference data will be continuously captured during the intervention. We will randomize 80 older Latinos from the Chicago Latino community to either an ecological momentary intervention using fitbits (n=40) or to physical activity guidelines (n=40).

Study interaction 1-baseline test (Approximately 2 hours). Participants will be screened for inclusion/exclusion criteria. If criteria for inclusion in the study are met participants will undergo informed consent process. Following informed e-consent conducted via zoom video/telephone participants will be asked about their demographics (demographic

form), and contact information (Face sheet), and then they will be asked about their medical history. Following the medical history we will fill out the Charlson co-morbidity questionnaire, and conduct the following cognitive function measures as approved by the NIH for use via video call: a. Picture vocabulary test, b. Picture sequence test, c. List sorting test, d. Oral reading recognition test, e. Auditory verbal learning test, and the Trail Making test A and B. Following the cognitive function testing, we will conduct a phone/video interview. The interview will be recorded, analyzed and used to develop the intervention.

Following the interview we will conclude the phone call and send the participants an activity monitor to be worn on the waist for 8 days to measure sedentary time: The participants will mail the monitor back to us after 8 days. Once we have received the physical activity monitor we will randomize the participant to intervention or control.

**Optional in-person visit (approximately 1 hour) If the participant is willing and able to undergo an MRI scan. No contrast will be used.**

- The MRI Visit will take place about one-week after the initial phone call. Participants will come to the Magnetic Resonance Imaging Center, 3T research center [name] and return the actigraph to us. We will ask participants to do the following:
  - Have an MRI to take pictures of the brain at a scanning facility. Scanning will last approximately 1 hour during.
  - Before entering the MRI room, participants will be asked to remove from all metal objects, including jewelry, watches, hair holders, or eyeglasses; and asked to empty pockets of all materials, including keys, wallets, and magnetic cards such as ATM and credit cards. In addition, if the clothing has more than a minimal amount of metal content, they may be asked to change into a hospital gown or other suitable garment. Finally, they may be asked to remove any eye shadow you may be wearing, because eye shadow sometimes contains metallic substances.
  - Because the MRI machine makes loud noises while it scans, a researcher or technician will provide participants with earplugs to reduce the noise level.
  - All of the procedures described above will be performed by qualified, licensed personnel and arranged at the participant's convenience. We will inform participants of any abnormalities found in the tests; however, the information obtained from the MRI and cognitive testing is experimental in nature and does not allow for clinical interpretation. We will, however, contact participants if the MRI or cognitive test results warrant a formal clinical follow-up and discuss this with their medical provider (e.g., General

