### **8.0 Data Collection and Management Procedures**

- We will use EMI designed to deliver content in real-time, and in the real-world environment. EMI, using a wearable sensor, an activity tracker and the Illumivu mEMA smart phone app, will enable real-time delivery of behavior options and real-time feedback on the effectiveness of behavior choices. This methodology will enable us to create a culturally appropriate intervention that is based on preferences of individuals within their community networks. Although the intervention will be guided by the focus group findings, in general, we expect that participants will wear a Fitbit that has been programmed to deliver a notification (a buzz) when activity has ceased for more than 10 minutes. They will receive a notification on their smartphone app with a suggestion on how to replace sitting time with PA such as standing up 5 times or taking 20 steps, or even performing a short preferred dance routine. We will capture Fitbit data in a real-time platform (ICardia). Participants will receive reminders from their smartphones to enter real-time feedback on the PA options selected and how successful they were in adopting the option. These data will allow us to track underlying preferences for behaviors and tailor the program accordingly. Participants will receive a message immediately with positive choices for behavioral action. Resulting actions and delivery of the intervention will be automatically captured and downloaded in real time.
- **Outcomes: Sedentary time** will be measured using the Actigraph, a validated tool for measuring sedentary time in older adults following standard procedures over 7 days at baseline and at follow up. Sedentary behavior will be defined as: 1) waking activity with an energy expenditure  $\leq 1.5$  metabolic equivalents occurring in a sitting or reclining posture; 2) vector magnitude counts are  $<70$  counts/15-s and vertical axis counts are  $<10$  counts/15-s. Sedentary interruption will be defined as counts  $>100$ /minute. Non-wear time will be considered to be 60 minutes of zero-activity counts. Any counts over 15,000 will be considered erroneous. A valid day will consist of 10 waking hours. At least 5 complete days of data must be available to be included in the analysis.
- **Cognitive and Physical Function Measures** will be assessed using the NIH Toolbox measures.

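### The baseline MRI visit, where the activity monitor is handed in, is timed too early for the 8-day wear period to be completed

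*Combined protocol and SAP*

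**What the plan says.** Section 6.0, Study interaction 1, has staff end the first call and then "send the participants an activity monitor to be worn on the waist for 8 days to measure sedentary time". The stated return route is the post: "The participants will mail the monitor back to us after 8 days". Receipt is the signal to allocate: "Once we have received the physical activity monitor we will randomize the participant to intervention or control".

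The optional in-person visit, described next in Section 6.0, has its own clock and its own return route. "The MRI Visit will take place about one-week after the initial phone call", and participants are to "return the actigraph to us" when they attend. Nothing ties the visit date to the end of wear, and the two return routes are not reconciled.

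Section 8.0 defines the sedentary-time outcome as measured "following standard procedures over 7 days at baseline and at follow up", counts a day as valid at 10 waking hours, and adds: "At least 5 complete days of data must be available to be included in the analysis".

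At follow-up (Section 6.0, Study interaction 3) the order is different. The monitor is worn for 8 days and mailed back. Only after it is received do the interview, the repeat cognitive tests and the repeat optional scan take place.

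**The concern.** The wear period and the MRI visit are both timed from the first call. The wear period alone is longer than the stated interval to the visit, before any delivery time is allowed for. Staff who keep to the visit timing and collect the monitor there cut the baseline recording short.

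Three things are at stake.

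- **Comparability.** Sedentary time is the first outcome listed in Section 8.0. MRI participants would have a short baseline window and a full 8-day follow-up window, while the others have 8 days at both.
- **Missing data.** A participant with fewer than five complete days drops out of the sedentary-time analysis. Because receipt of the monitor leads to randomisation, with no stated check of valid days, the shortfall may be noticed only after the intervention has begun. A pre-intervention baseline cannot be collected then.
- **Feasibility reading.** Aim 2 in Section 3.0 concerns the feasibility and acceptability of the activity measures. Short wear forced by the schedule could be mistaken for poor wear compliance.

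**Working it through.** **Inputs**

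- First call = day 0. The monitor is sent after it (Section 6.0).
- MRI visit and hand-in on day V. The stated timing gives V = 7, and it is approximate (Section 6.0).
- Prescribed wear: 8 days (Section 6.0).
- Outcome window: 7 days. Minimum for analysis: 5 complete days. Valid day: 10 waking hours (Section 8.0).
- Delivery time m, in days: not in the documents. Assumed range 0 to 5.

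**Formulas**

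- Full days strictly between arrival and visit: days m+1 to V-1, which is V - m - 1. At V = 7 this is 6 - m.
- Lenient count, in which the arrival day and the visit day together yield one more valid day: V - m. At V = 7 this is 7 - m.

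**Can the plan's 8 days be reached at day 7?** Full days: 6 - m ≥ 8 needs m ≤ -2. Lenient: 7 - m ≥ 8 needs m ≤ -1. Neither is possible. Days 0 to 7 touch eight calendar dates only if the monitor is in hand on the day of the call, and the first and last of those are part-days.

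**Wear days available at V = 7**

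| Delivery m | Full days | Lenient | 5-day minimum |
|---|---|---|---|
| 0 | 6 | 7 | met, 1 to 2 days spare |
| 1 | 5 | 6 | met, 0 to 1 day spare |
| 2 | 4 | 5 | met only on the lenient count, 0 spare |
| 3 | 3 | 4 | not met |
| 4 | 2 | 3 | not met |
| 5 | 1 | 2 | not met |

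The 7-day window of Section 8.0 is reached only with same-day delivery and lenient counting.

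**Sensitivity to the approximate timing**

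- V = 8: full days are 7 - m and lenient days 8 - m. The 5-day minimum is met for m ≤ 2 (full) or m ≤ 3 (lenient). Eight days is reached only with same-day delivery and lenient counting.
- V = 10: full days are 9 - m and lenient days 10 - m. Eight days is reached for m ≤ 1 (full) or m ≤ 2 (lenient).

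**Earliest visit that allows 8 wear days:** day m+8 (lenient) to m+9 (full). That is day 9 to 10 for m = 1, day 10 to 11 for m = 2, and day 11 to 12 for m = 3.

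**The case against.** The strongest reply is that this is loose wording which a scheduler will absorb. The visit timing is approximate, Section 6.0 lets the scan procedures be timed to suit the participant, and pairing the visit with hand-in suggests it was meant to fall near the end of wear. At day 10 the 8 days can be completed with quick delivery. The trial is also a feasibility pilot with mainly descriptive analyses, and the visit is optional. This limits the consequence. It does not remove the conflict, because the wording as it stands gives staff a visit date earlier than the end of wear and no rule for choosing between them.

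A reader might infer four stronger things that the documents do not support.

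- **That MRI participants cannot meet the analysis rule.** At day 7 the five-day minimum can still be met with delivery in about 1 to 2 days: 5 full days at m = 1, or 5 on the lenient count at m = 2. The documents give neither a delivery method nor a delivery time, so failure is a risk and not a certainty.
- **That allocation is harmed.** No eligibility, stratification or allocation rule uses baseline sedentary time. The truncation precedes randomisation and does not favour either arm.
- **That a planned analysis linking sedentary time to brain measures is damaged.** Sections 9.0 and 12.0 specify no such analysis.
- **That follow-up has the same fault.** There the monitor is already received before the optional scan is repeated.

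**Conclusion.** The concern holds as a scheduling contradiction within Section 6.0. At the stated day 7, the 8-day wear cannot be completed for any delivery time. Following the visit timing leaves 6, 5, 4 or 3 full wear days for delivery in 0, 1, 2 or 3 days, or one more if part-days count. Baseline wear is therefore shorter for MRI participants than for the others and than at their own follow-up. The five-day minimum has at most one spare day with next-day delivery, and is missed from about 3 delivery days.

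The size of the shortfall rests on two things the documents leave open: the delivery time, which is assumed here, and how far the approximate visit timing may stretch. The effect is confined to the optional MRI group at baseline. It amounts to lost or non-comparable baseline data, not bias between arms.

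**What to change.** Reconcile the two instructions in Section 6.0. Schedule the baseline MRI visit on or after completion of the 8th wear day and before randomisation, in place of a date counted from the first call. If the scanner slot falls earlier, state that the participant keeps the monitor, finishes the 8 days and mails it back, as non-MRI participants do. On either route, receipt of the monitor then triggers randomisation only after the full wear period has passed.

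The cost is a change of wording and a baseline MRI visit a few days later (about day 9 to 12 for delivery in 1 to 3 days, against day 7 now). No change is needed at follow-up.
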